Clinical Investigation Plan

CP363

Clinical Investigation Exploring Two Ostomy Product Prototypes

November 2023-March 2024

Master

ClinicalTrials.gov ID: NCT06237686

Approval date of version 2.0: 2023/12/19

CHANGE LOG

VERSION NUMBER	ISSUED BY (INITIALS)	COMMENTS (MAJOR CHANGES SINCE LAST REVISION)
1.0	[REDACTED]	First approved version
2.0	[REDACTED]	[REDACTED]

This confidential document is the property of Coloplast A/S.
No unpublished information contained herein may be
disclosed without written approval of Coloplast A/S.

SYNOPSIS OF THE CLINICAL INVESTIGATION

Title

Clinical Investigation Exploring Two Ostomy Product Prototypes

Test products

Two ostomy product prototypes (Test product A and B) will be tested in this investigation.

Intended use

The test products are intended to be used in the same manner as a CE-marked ostomy product.

Objective(s)

Primary objective

The primary objective is to investigate Test product A and B's ability to swell around the stoma.

Secondary objective

The secondary objective is to investigate the peristomal skin condition after wearing Test products A and B for 4 hours.

Design of the investigation

The clinical investigation is a non-comparative, one-sequence, open-labelled, single-centre study.

Expected duration of the clinical investigation

All subjects will test both Test product A and B, with a minimum of 7 days apart. In total, each subject will be enrolled in the investigation for 8 days +3 days.

Primary endpoint and secondary endpoint(s)

Primary endpoint

The Test product formulation's ability to swell at the end of each test period (assessed by photos and video by qualitative evaluation).

Secondary endpoint

The change in pain, itching and burning (PIB) score (0-10) based on Peristomal Skin Health (The Ostomy Skin Tool 2.0) from before to after end use of the Test products.

- Adverse events

Population/subjects

As this is an exploratory investigation with a qualitative primary outcome no formal sample size is calculated but it is evaluated that 10 subjects with an ileostomy (liquid output) will be adequate to investigate the Test product A and B's ability to swell around the stoma.

Inclusion criteria		Exclusion criteria	
To be included in this investigation the subject must answer yes to the following inclusion criteria's:		To be included in this investigation the subject must answer no to the following exclusion criteria's:	
1.	Has given written informed consent	1.	Is currently receiving or have within the past 60 days received radio- and/or chemotherapy (Low doses radio- and/or chemotherapy (Assessed by Principal Investigator) is allowed. for indications other than cancer)
2.	Is at least 18 years of age and has full legal capacity	2.	Is currently receiving or have within the past 30 days received topical steroid treatment in the peristomal skin area, e.g. lotion or spray or systemic steroid (tablet/injection) treatment
3.	Has had an ileostomy for more than 3 months	3.	Is pregnant or breastfeeding
4.	Has suitable peristomal skin area (assessed by investigator)	4.	Has dermatological problems in the peristomal area (assessed by investigator)
5.	Is currently using flat SenSura Mio 1-piece or 2-piece	5.	Participates in other clinical investigations. Exception: Participation in other Coloplast sponsored clinical investigations is accepted under the circumstances that the subject has paused the activities in the investigation and are otherwise complying with the inclusion and exclusion criteria of this protocol
6.	Has used flat SenSura Mio 1-piece or 2-piece for at least 14 days	6.	Has any known allergies towards ingredients in the investigational device
7.	Has a stoma size less than 45mm in diameter		

LIST OF ABBREVIATIONS

ABBREVIATION	WRITTEN OUT	EXPLANATION
ADE	Adverse Device Effect	See section 18.2
AE	Adverse Event	See section 18.1
ASADE	Anticipated Serious Adverse Device Effect	See section 18.4.2
CIP	Clinical Investigation Plan	
CRF	Case Report Form (paper or electronic)	Questionnaire to be used for data collection
CM	Clinical Manager	
DQF	Data Query Forms	A DQF is a query specifically used in clinical research. The DQF is the primary data query tool from the sponsor to clarify discrepancies and ask the investigator for clarification. The DQF is part of the data validation process in a clinical investigation.
DD	Device deficiency	
EC	Ethics Committee	
IB	Investigator's Brochure	Compilation of the current clinical and non-clinical information on the investigational medical device(s,) relevant to the clinical investigation.
IFU	Instruction For Use	
ITT	Intention to Treat	

1.2. Investigators

The CM is responsible for maintaining an updated list of all PIs, investigation sites and institutions.

PRINCIPAL INVESTIGATOR

In case of emergency, please contact the CM from the above list of sponsor representatives.

2. Rational/justification for conducting the clinical investigation

Peristomal skin complications (PSCs) are the predominant complication for people living with a stoma, which affect their quality of life negatively (1).

Especially among people living with an ileostomy or colostomy with liquid faecal effluent, the incidence of PSCs is high (2, 3), which may be ascribed to the presence of a high content of digestive proteolytic enzymes and other chemical irritants in the liquid and corrosive effluent (4-6). Some of the common clinical signs of PSCs include pain, itching, burning, discolouration, bleeding, and wounds (3).

Among the main reasons for developing PSCs are that the peristomal skin is exposed to stomal output either due to leakage of output under the baseplate and/or imperfect cutting of the hole in the baseplate, and incorrect application creating a gap between the hole in the baseplate and the stoma (2, 3, 7).

The aim of the present investigation is to explore the properties of two different ostomy product prototypes (Test products A and B) during use.

The data from this explorative investigation will be used for further optimization and development of the prototypes.

3. Objective(s) and hypotheses of the clinical investigation

3.1. Objective (s)

Primary objective

The primary objective is to investigate Test product A and B's ability to swell around the stoma.

Secondary objective

The secondary objective is to investigate the peristomal skin condition after wearing Test product A and B for 4 hours.

3.2. Hypotheses

This is an exploratory investigation and there is no formal success and/or fail criteria and no formal hypotheses applied in this investigation. It is expected that the results of this investigation will provide valuable in-sight to the further optimization and development of the Test products (prototypes).

[figure not shown]
4. Investigational device and comparator(s)

Two ostomy product prototypes (Test product A and B) will be tested in this investigation.

4.1. Description of investigational device

The Swellertech formulations of Test product A and B are characterized as followed:

Below in fig. 1 a schematic drawing of the test product is shown.

4.1.1. Manufacturing

Coloplast A/S [REDACTED] is legal manufacturer of the test products.

4.2. Identification and traceability of the device

The test products will be identified as CP363/A and CP363/B.

Investigational device label can be found in Investigators Brochure (8)

4.3. Intended use of the device in the clinical investigation

The test products are intended to be used in the same manner as a CE-marked ostomy product.

4.4. Intended population for the device

The population will consist of 10 subjects with an ileostomy (liquid output). To be enrolled in the investigation, subjects must comply with the Eligibility criteria's in section 6.1.

4.5. Handling of the investigational device

Handling of the test products do not require specific competencies other than health care professional basic training. The test products will only be handled by study personal, who will receive training in study conduct during SIV.

Further details can be found in the IB (9)

4.6. Total number of devices intended for the clinical investigation

Each subject is expected to use one of each Test product A and B during their participation in the investigation.

This gives:

- $1 \times 10 = 10$ Test product A

- $1 \times 10 = 10$ Test product B

Additionally, an extra buffer of 10 x each Test product will be produced.

In total, 20 of each Test product A and B needs to be released for the investigation.

4.7. Description of the comparator product(s)

No comparator is used in this investigation.

5. Design of the clinical investigation

5.1. General

The clinical investigation is a non-comparative, one-sequence, open-labelled, single-centre study.

All subjects will test both Test products A and B with a minimum of 7 days apart. In total, each subject will be enrolled in the investigation for 8 days +3 days.

The study will consist of:

- V0: Information visit
- V1: Inclusion of subjects, baseline registrations and Test visit 1 (Testing Test product A)
- V2: Test visit 2 (Testing Test product B) and Termination visit

V0 and V1 can be conducted on the same day.

The test period of each Test product (A and B) is set to 4 hours. The total duration of each visit (V1 and V2) is set to approximately 5 hours. Subjects will leave each test visit using only their usual stoma product.

[figure not shown]

Figure 2 Schematic view of investigation

5.2. Primary endpoint

The Test product formulation's ability to swell at the end of each test period (assessed by photos and video by qualitative evaluation).

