5.7. Randomisation Procedure

Not applicable

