5.8. Blinding

Not applicable

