7.1. Clinical investigation-related procedures

Visit 0

- Introduction to the investigation

[figure not shown]
Visit 1 (It is possible to perform V0 and V1 on the same day)

- Informed Consent Form signed
- Register date of visit
- Allocate subject number
- Check of inclusion and exclusion criteria, including pregnancy test, if applicable
- Registration of baseline data
 - Age [years]
 - Gender [Male/Female]
 - Height [cm]
 - Weight [kg]
 - Year of creation of stoma [year]
 - What was the reason for creation of your stoma [Morbus Crohn, Colitis ulcerosa, Cancer, Other (text)]
 - What is your current product size (baseplate size) - Length [mm], Width [mm]
 - What type is your current SenSura® Mio product? [1-piece/2-piece]
 - Which stoma accessories do you normally use? (You may tick more than one box) [None/Adhesive remover/Paste/Rings/Stoma tape/Stoma belt/Hernia belt/Stoma powder/(Barrier lotion/cream/spray/wipes)/(Cleansing wipes/cleansing spray)/Odour remover/Other accessories (text)]

[figure not shown]
Use of accessories are allowed as long as they are not used in the area around the stoma (~3-5 mm) during visits.

Visit 1-2 (Testing Test product A and B)

- Visual inspection of whether the subject has suitable peristomal skin area for the test (assessed by Investigator, or designee). If the peristomal skin is deemed unsuitable for the test the visit must be rescheduled (if the subject has been rescheduled twice and the peristomal skin is still not deemed suitable for the test the subject will be terminated and replaced)
- Subject questions regarding the perception/condition of their peristomal skin (PIB)
- Measure the diameter of the subject's stoma (done by Investigator, or designee)
 - Diameter of the stoma on the widest place [mm]
 - Diameter of the stoma on the smallest place [mm]
 - Shape of the stoma [Round/Oval/Irregular]
- Take photos of the peristomal skin before application of the Test product
- Take photos of the Test product when cut to fit the stoma (adhesive site)

- Just before removal of the Test product ask the subject to complete questions regarding the perception/condition of their peristomal skin (PIB)

- Assess the subject's wellbeing and compliance with the CP363 clinical investigation plan
- Assess and record any deviations and adverse events
- Record any given concomitant medication
- Perform device accountability
- Schedule next visit

Addition to Visit 2 (Testing Test product B) - Termination visit

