11.1. Data collection procedure

All assessments and observations throughout the investigation for each subject must be carefully recorded in an eCRF or in a paper CRF (pCRF) during the visit or immediately after. The eCRF makes it possible to enter data right away when they are obtained. This is the preferred way of collecting data. In case this is not possible the data should be entered no later than seven days after the visit / procedure.

When subject and investigator is required to complete different sections in the CRF, it will be specified which sections the subject will fill in (using paper CRF or app solution) and which sections the investigator will fill in.

In the unforeseen situation, where site cannot establish connection to the EDC system, a paper CRF (pCRF) has been printed and supplied by sponsor.

If for some reason [REDACTED] is not available the subject must complete the questionnaire on the paper CRF, and the data must be entered into the eCRF by site personnel.

Qualitative evaluations will be registered in an Excel Sheet, that will be saved in the Data Management archive site with data management access only. Only the overall conclusions will be registered in the eCRF.

Photos and video records will be saved in the Data Management archive site with data management access only.

The remaining endpoints, assessment, backup measurements and baseline information can be entered directly into the eCRF.

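### The plan makes no provision for masked reading of the photos and video behind its subjective primary endpoint, although coded, random-order reading looks practicable at low cost

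*Combined protocol and SAP*

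**What the plan says.** Section 5.2 defines the primary endpoint as the formulation's swelling when each test period ends, "assessed by photos and video by qualitative evaluation". It names no reader, scale or reading order.

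Section 5.1 gives the design: "The clinical investigation is a non-comparative, one-sequence, open-labelled, single-centre study". The same section assigns product A to visit 1 and product B to visit 2 for every subject. Section 5.7 states that randomisation does not apply. The whole of section 5.8, on blinding, is "Not applicable".

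On the images, section 11.1 says: "Photos and video records will be saved in the Data Management archive site with data management access only". The qualitative evaluations go into an Excel sheet in the same archive, and only overall conclusions go into the eCRF. Section 10.1 has endpoints summarised separately for each test product. Section 2 gives the use of the data as further optimisation and development of the prototypes.

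**The concern.** A qualitative judgement of swelling leaves room for the reader's expectation. A reader who knows which prototype is shown, and who has a view on which formulation should swell more, may resolve doubtful images in that direction. The study has no comparator (section 4.7), so nothing in the design would reveal a general tendency to see swelling.

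The open label applies to wear: the subject and the site staff know the product. It does not settle how stored images are read. They can be separated from their labels after the visit, and the plan does not use that opportunity or say why not. At stake is the trustworthiness of the only primary result, as a description of each prototype and as input to further development.

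**Working it through.** There is no planned figure to reproduce. The sample size of 10 has no formal calculation (section 10.2), and masking does not change it. The check sets the sections side by side.

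1. **Is the endpoint subjective?** Yes. Section 5.2 calls for a qualitative evaluation and gives no scale or measurement rule.

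2. **Is masked reading provided for?** No. Section 5.8 declines blinding without qualification. Section 11.1 covers storage, the Excel sheet and the eCRF entry, but not coding, masking or reading order. Restricted access to the archive is a storage rule. It limits who can open the files but does not remove product or visit from them.

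3. **Would the product be identifiable by default?** Yes, from visit or date. Under section 5.1, visit 1 means A and visit 2 means B for every subject, and section 4.2 gives the products open A and B identifiers. Any visit number or date attached to an image therefore reveals the product.

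4. **Does the result feed something by product?** Yes. Section 10.1 summarises by test product, and section 2 sends the results into prototype development.

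5. **How large is the reading task?** Section 6 requires 10 completers, each testing two products:
   - end-of-period sets: 10 × 2 = 20;
   - if each is paired with a pre-use set as reference (assumed): 20 × 2 = 40.

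   Replaced subjects who wore a product before leaving could add a few sets. This is a small load for one reader.

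6. **Could the existing pre-use photos be mixed in as unswollen controls?** Not on the visible text. Section 7.1 lists photos of the peristomal skin before application, and then: "Take photos of the Test product when cut to fit the stoma (adhesive site". The first shows no product and the second shows the adhesive side of an unworn product. Neither shows an unswollen product in place around the stoma, and a reader would tell both from an end-of-wear image.

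7. **Can the bias be sized?** No. That would need a defined swelling category and the share of readings that expectation changes. The documents give neither.

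**The case against.** The strongest reply is that no section says who reads the images, when, or with what information. The public text of section 7.1 is also incomplete: the end-of-period photo and video steps are not visible, and their absence cannot be held against the plan. This stands. A reader might infer that the evaluator knows both product and time point. The documents do not establish either. The inference is strong for product, because of the open label and fixed order, and weaker for time point. What remains is that section 5.8 rejects blinding outright and section 11.1 provides no coding.

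A second reply is that the study is exploratory and non-comparative, without hypotheses (section 3.2) or pass/fail criteria (section 10.4). This lowers the stakes but does not protect the result, since expectation acts on each product's own reading. A reader might also infer that the data serve to choose between A and B. The documents do not say so; they speak only of optimisation and development.

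A third reply is that swelling is a change, so the reader may need the subject's pre-use image. This stands too, and rules out shuffling single images without their reference. It does not rule out hiding the product.

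Finally, the documents do not show whether A and B look alike. If they differ visibly, masking will be incomplete.

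**Conclusion.** The point holds as a gap in the plan: a subjective sole primary endpoint, blinding declined, no masked reading provided for, and a fixed order that reveals the product through visit or date. Coded, random-order reading is the better method and looks practicable for about 20 sets.

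The size of any bias is unknown. With 10 readings per product, one altered reading would move a proportion by 1/10 = 10 percentage points, and a reader might infer a shift of 10 to 30 points from one to three altered readings. The documents do not support that figure. They define no yes/no category and no swelling rate, and the number of doubtful readings would be an assumption.

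The conclusion assumes that the evaluation can be made from the stored photos and video, as section 5.2 implies, and that no coding procedure exists in text that is not public. It merits a change to the plan, but the exploratory purpose keeps the consequence modest.

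**What to change.** In sections 5.2, 5.8 and 11.1, name the reader's role and state that:

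- data management exports the end-of-period photos and video under a random code, without product, visit or date;
- where a pre-use image is needed as a reference, it stays paired with its end-of-period set under the same code;
- the planned reader evaluates the sets in random order and enters each evaluation in the Excel sheet before the code is opened;
- pre-application images are not mixed in as negative controls.

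If the sponsor judges this infeasible, section 5.8 should give the reason.

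The cost is a coding list and some file handling. No extra subject, visit, image or reader is needed. The documents give no cost figure, so calling this cheap is a judgement based on the small number of sets. Masking may be only partial if A and B look different or if the reader attended the visits. Coding also leaves product confounded with visit, because A always comes first.

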5.3. Secondary endpoints

The change in pain, itching and burning (PIB) score (0-10) based on Peristomal Skin Health The Ostomy Skin Tool 2.0 (OLS 2.0) from before to after end use of the Test products.

The questions of experienced PIB underneath the centre part of the baseplate from the OST 2.0 are (see Appendix 1):

- Please rate on a scale from 0-10 how itchy the skin around your stoma has been at its worst since you last changed your product (rated on a scale from 0-10, where 0 is no itch and 10 is worst possible peristomal skin itch).
- Please rate on a scale from 0-10 how painful the skin around your stoma has been at its worst since you last changed your product (rated on a scale from 0-10, where 0 is no pain and 10 is worst possible peristomal skin pain).
- Please rate on a scale from 0-10 any burning feelings from the skin around your stoma at its worst since you last changed your product (rated on a scale from 0-10, where 0 is no burning and 10 is worst possible peristomal skin burning).

- Adverse events

5.5. Rationale for selection and measurement of endpoints

It is expected that the selected endpoints will provide valuable in-sight to the further optimization and development of the test products (prototypes).

5.6. Equipment

- Ruler
- Camera

5.7. Randomisation Procedure

Not applicable

5.8. Blinding

Not applicable

5.9. Total expected duration of the clinical investigation

The dates below are approximate, and no subjects will be enrolled before all required approvals have been obtained. If changes are required, applicable EC will be notified.

First subject enrolled (12/2023)

Last subject enrolled (02/2024)

Last subject complete (02/2024)

Final report (02/2025)

6. Clinical Investigation population

The population will consist of 10 subjects with an ileostomy (liquid output) enrolled at one clinical investigation site. Screening failures and subjects who withdraw or are prematurely terminated from the investigation will be replaced until 10 subjects have completed the study.

6.1. Eligibility criteria

To be included in the investigation, the subjects must comply with the selection criteria described below.

6.1.1. Inclusion criteria

Inclusion criteria		Justification for inclusion criteria
To be included in this investigation the subject must answer yes to the following inclusion criteria:		
1.	Has given written informed consent	To meet the Helsinki declaration
2.	Is at least 18 years of age and has full legal capacity	To meet the Helsinki declaration
3.	Has had an ileostomy for more than 3 months	To ensure subjects are recovered from stoma surgery
4.	Has suitable peristomal skin area (assessed by investigator)	To be able to have [REDACTED]
5.	Is currently using flat SenSura Mio 1-piece or 2-piece	To ensure that the subjects are used to standard Coloplast adhesive
6.	Has used flat SenSura Mio 1-piece or 2-piece for at least 14 days	To ensure that the subjects are used to standard Coloplast adhesive
7.	Has a stoma size less than 45mm in diameter	To ensure Test product fits around the stoma

